19.3. Source data

The primary source documents for this study will be the patient's medical records and all rating scale CRFs and worksheets used to directly record assessment scores for 24-hour patient home diary, MMSE, MDS-UPDRS, UDysRS, CGI-C and C-SSRS throughout the study. If separate research records are maintained by the Investigator(s) both the medical record and the research records should be monitored/audited for the purpose of the study.

A separate source data agreement will be generated at the study site before start of enrolment, specifying the location of the source of derived information appearing in the CRF. This document must be signed by the Principal Investigator and the Monitor to confirm agreement before start of recruitment.

The Investigator should guarantee access to source documents to the Monitor, Competent Authorities and the IECs/IRBs, as required.

19.4. Study agreements

The Principal Investigator must comply with all the terms, conditions, and obligations of the Clinical Study Agreement (CSA) for this study.

Confidential	Version: 5.0	Page 70 of 74
Protocol: IRL790C005	Date: 5 Mar 2021	e

Agreements between Sponsor and the study sites must be in place before any study-related procedures can take place, or patients be enrolled.

19.5. Study timetable and end of study

The end of the clinical part of the study is defined as the last visit of the last patient participating in the study.

The study is expected to start in Quarter 3, 2020 and to be completed by Quarter 1, 2022.

20. QUALITY ASSURANCE

Authorized representatives of Sponsor, Competent Authority (CA) or IEC/IRB may perform audits or inspections at the study site, including SDV. The purpose of an audit or inspection is to systematically and independently examine all study-related activities and documents, to determine whether these activities were conducted and data were recorded, analyzed, and accurately reported according to the Clinical Study Protocol, ICH GCP (ICH E6 (R2) guidelines and any applicable regulatory requirements. The Investigator will contact the Sponsor immediately if contacted by a CA about an inspection at the study site.

21. INSURANCE

Appropriate insurance cover has been secured in favour of patients participating in clinical trials. The cover is provided to the patient on terms and conditions of the clinical trial insurance. Insurance cover exists for health damages as a result of measures carried out in connection with the clinical trial.

22. CONFIDENTIALITY

Any confidential information relating to the IMP or the study, including any data and results from the study, will be the exclusive property of the Sponsor. The Investigators and any other persons involved in the study will protect the confidentiality of this proprietary information belonging to the Sponsor.

The Investigator must assure that patient's anonymity will be provided. The Investigator will keep a separate list with at least the initials, the patient's study number, names, addresses and telephone numbers. The Investigator will maintain this for as long as requested by the Sponsor.

Details of access to the patients' data, conforming to the requirements of the General Data Protection Regulation (GDPR) 2016/679 and other applicable regulations will be fully described within the patient information sheet. The consequence of the patients' withdrawal of consent with regards to the use of data will also be described.

23. PREMATURE TERMINATION OF THE STUDY

The Sponsor reserves the right to discontinue the study at any time but intends only to exercise this right for valid scientific or administrative reasons.

Confidential	Version: 5.0	Page 71 of 74
Protocol: IRL790C005	Date: 5 Mar 2021	C

After such a decision, the Investigator must inform all participating patients and perform relevant assessments, preferably according to the scheme for the final assessments. All delivered and unused IMP and other study materials must be returned and all CRFs completed as far as possible.

24. RECORD RETENTION

After completion of the study, all documents and data relating to the study will be kept in an orderly manner by the Investigator in a secure study file.

Essential documents must be retained for at least two years after the final marketing approval in an ICH region or until two years have elapsed since the formal interruption of the clinical development of the product under study.

It is the responsibility of the Sponsor to inform the Investigator of when these documents can be destroyed. The Investigator must contact the Sponsor before destroying any trial-related documentation. In addition, all patients' medical records and other source documentation will be kept for the maximum time permitted by the institution.

25. PUBLICATION OF RESULTS

25.1. Clinical study report

Sponsor will post clinical trial results in the EudraCT and ClinicalTrials.gov database within the required timeline.

A Clinical Study Report, in compliance with ICH E3; *Structure and content of Clinical Study Reports*, describing the conduct of the study, the statistical analysis performed, and the results obtained, will be prepared. The report will be reviewed and approved by, as a minimum, the Statistician and the Sponsor.

25.2. Annual safety report

The Sponsor will submit an annual safety report to the CA and to the IEC/IRB. The report shall summarise all SAEs and contain an update of the risk-benefit evaluation if there has been any change since the approval of the clinical study.

25.3. Confidentiality and ownership of study data

Any confidential information relating to the IMP or the study, including any data and results from the study will be the exclusive property of the Sponsor. The Investigator and any other persons involved in the study will protect the confidentiality of this proprietary information belonging to the Sponsor.

25.4. Publication

The Sponsor is entitled to publish and/or present any results at scientific meetings, and to submit clinical trial data to national and international Regulatory Authorities. The Sponsor reserves the right to use such data for commercial purposes.

Confidential	Version: 5.0	Page 72 of 74
Protocol: IRL790C005	Date: 5 Mar 2021	C

The results from this study will be submitted for publication only at the discretion of the Sponsor.

This document is the property of Worldwide Clinical Trials Inc. and may not be duplicated, copied, altered or removed from company without prior approval from Worldwide Quality Assurance or in compliance with Worldwide Standard Operating Procedures.

REF: Worldwide-TMP-QA-001f-1.3

Governing QMD: Worldwide-SOP-ST-001

Worldwide Clinical Trials Controlled Quality Management Document		
CLINICAL TRIALS	Sponsor:	Integrative Research Laboratories Sweden AB
	Protocol Number:	IRL790C005
STATISTICAL ANALYSIS PLAN. PHASE 2-3-4		

STATISTICAL ANALYSIS PLAN. PHASE 2-3-4

Abbreviation	Description
NTEAE	Non-Treatment-Emergent Adverse Event
PD	Parkinson's Disease
PDev	Protocol Deviations
РК	Pharmacokinetic
PPS	Per Protocol Set
PT	Preferred Term
SAP	Statistical Analysis Plan
SAS	Safety Analysis Set
SD	Standard Deviation
SDTM	Study Data Tabulation Model
SE	Standard Error
SI	Système International
SOC	System Organ Class
TEAE	Treatment-Emergent Adverse Event
WHO Drug	World Health Organization Drug Dictionary

QMD Ref: Worldwide-TMP-ST-005-7.0 Effective: 12Aug2019	Governing QMD: Worldwide-SOP-ST-001		
Confidentiality Statement			
This document is the property of Worldwide Clinical Trials Inc. and may not be duplicated, copied, altered or removed from company without prior approval from Worldwide Quality Assurance or in compliance with Worldwide Standard Operating Procedures.			
DEE: Worldwide TMD OA 001f 1 2	Dage 7 of 40		

Worldwide Clinical Trials Controlled Quality Management Document		
CLINICAL TRIALS	Sponsor:	Integrative Research Laboratories Sweden AB
	Protocol Number:	IRL790C005
STATISTICAL ANALYSIS PLAN. PHASE 2-3-4		

1 **INTRODUCTION**

This document details the planned statistical analyses for Integrative Research Laboratories Sweden AB, protocol "IRL790C005" study titled "A Randomized, Double-Blind, Placebo-Controlled Phase IIb Study Evaluating the Efficacy of Mesdopetam on Daily ON-Time Without Troublesome Dyskinesia in Patients with Parkinson's Disease". The proposed analyses are based on the contents of protocol Version 5.0, dated 05 March 2021.

This is a multi-centre, randomized, double-blind, placebo-controlled study with the primary objective to evaluate the efficacy of 84 days' treatment with mesdopetam compared to placebo in patients with Parkinson's Disease (PD) exhibiting ON-phase dyskinesia.

The study comprises a screening period of up to 8 weeks, followed by a 12-week treatment period. A follow-up visit will be performed approximately 1 week after the last Investigational Medicinal Product (IMP) dose.

Patients will be randomized to receive one of three doses of mesdopetam (2.5 mg, 5 mg, or 7.5 mg) or placebo b.i.d. For patients to adjust to the new medication, a run-in phase with either 5 mg mesdopetam or placebo b.i.d. will take place during the first week (Day 1 evening dose to Day 9 morning dose).

A dose reduction is permitted if the patient manifests increased parkinsonism and/or a consistent increase in motor OFF-time. The dose can only be reduced once (and only by 2.5 mg b.i.d.). Dose reductions are permitted from Visit 2 until Visit 3 (i.e., Day 9 - Day 28), after which the reduced dose should be kept stable until end of treatment (EOT) period (Visit 5, Week 12).

2 **STUDY OBJECTIVES AND ENDPOINTS**

2.1 Primary Objective

• To evaluate the effectiveness of adjunctive treatment with mesdopetam dosed at 2.5 mg. 5 mg, or 7.5 mg b.i.d. (permitting a single 2.5 mg dose reduction to a minimum dose of 2.5 mg, up to Day 28) compared to placebo in patients with PD exhibiting troublesome ON-phase dyskinesia.

QMD Ref: Worldwide-TMP-ST-005-7.0 Effective: 12Aug2019	Governing QMD: Worldwide-SOP-ST-001	
Confidentiality Statement		
This document is the property of Worldwide Clinical Trials Inc. and may not be duplicated, copied, altered or removed from company without prior approval from Worldwide Quality Assurance or in compliance with Worldwide Standard Operating Procedures.		
REF Worldwide-TMP-OA-001f-1 3	Page 8 of 49	

Worldwide Clinical Trials Controlled Quality Management Document		
WORLDWIDE CLINICAL TRIALS	Sponsor:	Integrative Research Laboratories Sweden AB
	Protocol Number:	IRL790C005
STATISTICAL ANALYSIS PLAN. PHASE 2-3-4		

2.2 Secondary Objectives

- To establish the dose response relationship with 3 dose levels of mesdopetam.
- To evaluate the effects of mesdopetam on severity of ON-phase dyskinesia and motor symptoms of PD.
- To evaluate the effects of mesdopetam on the daily hours spent in different motor states.
- To evaluate the safety and tolerability of mesdopetam given twice daily during 84 consecutive days.
- To evaluate trough and 2-hour post dose plasma concentrations of mesdopetam and its two main metabolites (IRL902 (N-dealkylated) and IRL872 (acetylated)).

2.3 Exploratory Objectives

- To assess overall PD symptoms.
- To assess cognitive function.

3 ENDPOINTS

3.1 Primary Efficacy Endpoint

• Change in average daily hours of ON-time without troublesome dyskinesia with mesdopetam compared to placebo as assessed with 24-hour patient home diaries from baseline to end of treatment (EOT) (Visit 5, Week 12).

3.2 Key Secondary Efficacy Endpoints

- Change from baseline with mesdopetam compared to placebo in ON-phase dyskinesia assessed by MDS-UPDRS part 4 question 4.2 (Functional impact of dyskinesias).
- Change from baseline with mesdopetam compared to placebo in disability associated with ON-phase dyskinesia assessed with the sum score of parts 1b and 4 of the UDysRS.

QMD Ref: Worldwide-TMP-ST-005-7.0 Effective: 12Aug2019	Governing QMD: Worldwide-SOP-ST-001		
Confidentiality Statement			
This document is the property of Worldwide Clinical Trials Inc. and may not be duplicated, copied, altered or removed from company without prior approval from Worldwide Quality Assurance or in compliance with Worldwide Standard Operating Procedures.			
PEE: Worldwide TMD OA 001f 1 2	Page 0 of 40		

Worldwide Clinical Trials Controlled Quality Management Document		
WORLDWIDE CLINICAL TRIALS	Sponsor:	Integrative Research Laboratories Sweden AB
	Protocol Number:	IRL790C005
STATISTICAL ANALYSIS PLAN. PHASE 2-3-4		

3.3 Other Key Secondary Efficacy Endpoints

- Change from baseline with mesdopetam compared to placebo in motor symptoms of PD assessed with MDS-UPDRS total score of part 2 (M-EDL).
- Change from baseline with mesdopetam compared to placebo in average daily OFF-time.

3.4 Other Secondary Efficacy Endpoints

- Change from baseline in average daily hours spent in each motor state (ON-time without troublesome dyskinesia, ON-time with troublesome dyskinesia, OFF, and asleep) for each individual dose level (2.5 mg, 5 mg, 7.5 mg b.i.d.).
- Change from baseline with mesdopetam compared to placebo in ON-phase dyskinesia assessed with the sum score of the modified UDysRS (parts 1, 3 and 4).
- Change from baseline with mesdopetam compared to placebo in ON-phase dyskinesia assessed by MDS-UPDRS part 4 question 4.1 (Time spent with dyskinesias).
- Change from baseline with mesdopetam compared to placebo in average daily total ON-time (defined as the sum of ON-time with and without troublesome dyskinesia).
- Change from baseline with mesdopetam compared to placebo in Clinician's Global Impression of Severity (CGI-S) of ON-phase dyskinesia.
- Change from baseline with mesdopetam compared to placebo in the total score for the MDS-UPDRS Part 3, Motor Examination.

3.5 Exploratory Efficacy Endpoints

- Change from baseline with mesdopetam compared to placebo in CGI-S of overall PD symptoms.
- Change from baseline with mesdopetam compared to placebo in Total MMSE score.
- Change from baseline with mesdopetam compared to placebo in the total scores for component parts of the MDS-UPDRS (Part 1, and Part 4).

QMD Ref: Worldwide-TMP-ST-005-7.0 Effective: 12Aug2019	Governing QMD: Worldwide-SOP-ST-001		
Confidentiality Statement			
This document is the property of Worldwide Clinical Trials Inc. and may not be duplicated, copied, altered or removed from company without prior approval from Worldwide Quality Assurance or in compliance with Worldwide Standard Operating Procedures.			
DEE: Worldwide TMD OA 001f 1 2	Dage 10 of 40		

Worldwide Clinical Trials Controlled Quality Management Document		
WORLDWIDE CLINICAL TRIALS	Sponsor:	Integrative Research Laboratories Sweden AB
	Protocol Number:	IRL790C005
STATISTICAL ANALYSIS PLAN. PHASE 2-3-4		

• Change from baseline with mesdopetam compared to placebo in freezing and freezing of gait, assessed by MDS-UPDRS: Question 2.13 + Question 3.11.

3.6 Safety Endpoints

- Frequency and nature of adverse events (AEs), laboratory results, vital signs, physical examinations, Columbia-Suicide Severity Rating Scale (C-SSRS) and 12-lead electrocardiograms (ECG) at each visit from baseline to follow-up.
- Change from baseline with mesdopetam compared to placebo in features of dopamine dysregulation syndrome assessed by MDS-UPDRS Question 1.6.

3.7 Pharmacokinetic Endpoints

• Plasma concentrations of mesdopetam and its two main metabolites at pre-dose and 2 hours post-dose at 8 and 12 weeks of treatment.

4 SAMPLE SIZE

Analysis of the Phase IIa study Efficacy and Tolerability of IRL790 in 74 PD patients with levodopa-induced dyskinesia (LID) on stable antiparkinsonian medication (NCT03368170) suggested that daily ON-time with troublesome dyskinesia decreased to an observed difference of approximately 1.6 hours (p=0.0274) among treated patients (n=39) versus placebo (n=36). Doseresponse analysis suggested a dose dependent effect with an observed difference vs. placebo around 4.6 h at the 7.5 mg dose. A pooled standard deviation of 3.2-3.3 hours was observed among the doses studied. This observed data provided the assumptions for the sample size calculation.

140 randomized patients (35 per group) are thought to be enough to demonstrate a treatment difference of 3 hours with pooled standard deviation 3.5, between a single dose level of active treatment and control (i.e., 2.5 mg, 5 mg, or 7.5 mg mesdopetam vs placebo b.i.d.) for the primary endpoint with 92% power using a hierarchical testing strategy, with key secondary endpoints tested using a truncated Hochberg procedure with truncation parameter γ equal to 0.7 for the 7.5 and then the 5 mg doses and a standard Hochberg procedure for the 2.5 mg dose to maintain control of the family wise error rate (FWER) at the nominal 0.05 level.

QMD Ref: Worldwide-TMP-ST-005-7.0 Effective: 12Aug2019	Governing QMD: Worldwide-SOP-ST-001	
Confidentiality Statement		
This document is the property of Worldwide Clinical Trials Inc. and may not be duplicated, copied, altered or removed from company without prior approval from Worldwide Quality Assurance or in compliance with Worldwide Standard Operating Procedures.		
REF: Worldwide-TMP-QA-001f-1.3	Page 11 of 49	

Worldwide Clinical Trials Controlled Quality Management Document		
WORLDWIDE CLINICAL TRIALS	Sponsor:	Integrative Research Laboratories Sweden AB
	Protocol Number:	IRL790C005
STATISTICAL ANALYSIS PLAN. PHASE 2-3-4		

The sample size calculation was based on an expected dropout rate of 10%, i.e., assuming 31 patients per group will provide evaluable data on the primary endpoint at Week 12. The actual dropout rate was evaluated by the Sponsor after 70 randomized patients had completed Visit 3 (Week 4) and due to a higher-than-expected dropout rate, it was decided to increase the sample size to 154 (+10%) randomized patients as permitted by the protocol.

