6.15 Multiplicity

Multiple dose levels have been included in the study design to evaluate the dose-response relationship of mesdopetam with the hypothesis that the 7.5 mg b.i.d. dose will be the most efficacious of the dose levels studied.

Two key secondary endpoints (change from baseline in ON-phase dyskinesia assessed by MDS-UPDRS Question 4.2 and change from baseline in disability associated with ON-phase dyskinesia assessed with the sum score of UDysRS parts 1b and 4) will also be evaluated and thus a strategy for controlling the overall error rate whilst maintaining the planned study power is required.

To such aim, a hierarchical testing strategy will be used whereby first the 7.5 mg b.i.d. will be tested at a 5% level on the primary endpoint, and should the test be significant, the 2 key secondary endpoints will be tested for the 7.5 mg b.i.d. dose using a truncated Hochberg procedure with a truncation parameter $\gamma = 0.7$. This procedure works as follows for n = 2 tests:

- 1) p-values are sorted in ascending order as p_1 and $p_{2;}$
- 2) The largest p-value, p₂, is compared against the modified critical value c₂ below:

$$c_2 = \left[\frac{\gamma}{n-i+1} + \frac{1-\gamma}{n}\right]\alpha = \left[\gamma + \frac{1-\gamma}{2}\right]\alpha = \left[0.7 + \frac{0.3}{2}\right]0.05 = 0.0425$$

(where n = 2 and i = 2)

- 3) If $p_2 \le c_2$ then all key secondary hypotheses are rejected, otherwise the hypothesis associated with p_2 is retained and the other p-value, p_1 , is compared against the critical value c_1 , which can be obtained from the formula in 2) by replacing *i* with 1, leading to a critical value of 0.025;
- 4) If $p_1 \le c_1$ then the associated hypothesis is rejected, otherwise all hypotheses are retained and no more testing of primary or key secondary hypotheses for the lower doses is performed.

QMD Ref: Worldwide-TMP-ST-005-7.0 Effective: 12Aug2019	Governing QMD: Worldwide-SOP-ST-001		
Confidentiality Statement			
This document is the property of Worldwide Clinical Trials Inc. and may not be duplicated, copied, altered or removed from company without prior approval from Worldwide Quality Assurance or in compliance with Worldwide Standard Operating Procedures.			
phot approval nonit wondwide Quanty Assurance of in compnance with wondwide Standard Operating Proceedings.			
REF Worldwide-TMP-OA-001f-1 3	Page 40 of 49		

Worldwide Clinical Trials Controlled Quality Management Document		

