	Sponsor:	Integrative Research Laboratories Sweden AB
CLINICAL TRIALS	Protocol Number:	IRL790C005
STATISTICAL ANALYSIS PLAN. PHASE 2-3-4		

If at least one hypothesis is rejected in the above steps, then the primary endpoint is tested for the 5 mg b.i.d. dose at an alpha level that depends on how many hypotheses were rejected in the truncated Hochberg procedure and the truncation parameter γ .

To derive the amount of alpha level to carry over to the next level of testing, we account for how many hypotheses were rejected:

- a) If all or none were rejected, then we carry over, respectively, 0.05 (full α) or 0 (no α);
- b) If only one hypothesis were rejected, the amount of alpha to carry forward is given by:

$$((1-\gamma)|I|\alpha)/n = ((1-0.7)|1|0.05)/2 = 0.0075$$

Testing of the primary endpoint for the 5 mg b.i.d. dose is then conducted at the specified alphalevel and then, depending on the significance of this test, another truncated Hochberg procedure with the same truncation parameter is conducted for the key secondary endpoints, using the same alpha level carried over to test for the primary endpoint at 5 mg b.i.d. to derive the critical values for the testing using the same formulas shown above.

Once the truncated procedure has been conducted, the same approach to derive the amount of alpha that can be carried forward to the testing of the primary endpoint for the lower dose is then followed. Once this testing is complete, if the primary endpoint is significant at the pre-specified alpha level, the key secondary endpoints are tested using a standard Hochberg procedure, which is conducted similarly to its truncated version but with c_1 and c_2 being equal to $\alpha/2$ and α , respectively (where α is the significance level at which the primary endpoint was tested for the 2.5 mg b.i.d. dose).

An ordered tabulation of the endpoints tested, p-values observed, alpha-level tested against and acceptance or otherwise of the null hypothesis at each stage will be presented.

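### The 92% power in SAP section 4 is the power of the 7.5 mg primary test only; the hierarchy in SAP 6.15 gives 5 mg and 2.5 mg less

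*SAP*

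**What the plan says.** SAP section 4 assumes a 3 h difference and SD 3.5 between one dose and placebo, and gives the power as follows: "i.e., 2.5 mg, 5 mg, or 7.5 mg mesdopetam vs placebo b.i.d.) for the primary endpoint with 92% power using a hierarchical testing strategy". The same sentence goes on to name the truncated Hochberg steps and family-wise control at 0.05. The evaluable number comes from 10% dropout, "assuming 31 patients per group will provide evaluable data on the primary endpoint at Week 12". The section then reports that "due to a higher-than-expected dropout rate, it was decided to increase the sample size to 154 (+10%) randomized patients", but gives no new power.

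Protocol 14.2 has the same 92% as a plain two-tailed 0.05 comparison and does not mention a hierarchy there.

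SAP 6.15 sets the order of testing. The 7.5 mg primary comes first, at 5%, followed by two key secondaries at that dose. If neither is rejected, "otherwise all hypotheses are retained and no more testing of primary or key secondary hypotheses for the lower doses is performed". The next step reads "If at least one hypothesis is rejected in the above steps, then the primary endpoint is tested for the 5 mg b.i.d. dose". The alpha passed on is 0.05 if both key secondaries are rejected. A formula introduced by "If only one hypothesis were rejected, the amount of alpha to carry forward is given by" gives 0.0075 if only one is. The same scheme leads from 5 mg to 2.5 mg. The section gives the reason for the strategy as "a strategy for controlling the overall error rate whilst maintaining the planned study power is required".

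**The concern.** One power figure is attached to three doses and to a procedure that treats them unequally. A test that is run only after earlier tests succeed, and sometimes at a smaller alpha, cannot reject more often than the same test run alone at 0.05. The stand-alone figure is therefore a ceiling for 5 mg and 2.5 mg.

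This is the SAP's only numerical power statement, and establishing dose response is the first secondary objective listed. Someone weighing a non-significant or untested 5 mg or 2.5 mg result would take from section 4 that the comparison had 92% power under the procedure actually used.

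**Working it through.** **Inputs.** From SAP section 4: difference 3 h, SD 3.5, 31 evaluable per arm (35 × 0.9 = 31.5, taken as 31), overall alpha 0.05. Two-sided testing is from Protocol 14.2. The 1:1:1:1 allocation with one shared placebo arm is from SAP section 5, and the gates and carried alpha are from SAP 6.15.

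**Step 1: the plan's figure.** SE = 3.5 × √(2/31) = 0.889, and θ = 3/0.889 = 3.375. Power = Φ(3.375 − 1.960) = Φ(1.415) = 92.1% (91.3% with a two-sample t test). The stated 92% is reproduced.

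**Step 2: reduced alpha.** If one of two key secondaries is rejected, the carried alpha is (1 − 0.7) × 1 × 0.05 / 2 = 0.0075, with critical value 2.674. Stand-alone power is then Φ(3.375 − 2.674) = Φ(0.701) = 75.8%.

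**Step 3: upper bounds under 6.15.** Suppose every key-secondary gate opens and always passes on the full 0.05. The power for a dose is then the probability that its primary and all higher-dose primaries reject. Given the standardised placebo mean x, the dose comparisons are independent, so

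P = ∫ φ(x) × ∏ Φ(√2 (θ_j − 1.960) − x) dx,

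with the product over the doses down to the one in question and θ_j = (effect at dose j)/SE. A real key-secondary gate can only lower this.

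| Scenario (effects at 7.5 / 5 / 2.5 mg) | n per arm | 7.5 mg | 5 mg, at most | 2.5 mg, at most |
|---|---|---|---|---|
| 3 / 3 / 3 h, SD 3.5 | 31 | 92.1% | 86.6% | 82.3% |
| same, 154 randomized, 10% dropout, rounded down | 34 | 94.2% | 90.0% | 86.5% |
| same, unrounded | 34.65 | 94.6% | 90.6% | 87.3% |
| same, 154 randomized, no dropout | 38.5 | 96.4% | 93.6% | 91.2% |
| 4.6 / 3 / 3 h, SD 3.5 | 31 | 99.9% | 92.1% | 86.6% |
| 3 / 3 / 3 h, SD 3.3 | 31 | 94.7% | 90.8% | 87.6% |
| 3 / 3 / 3 h, SD 3.2 | 31 | 95.8% | 92.6% | 90.0% |
| 4.6 / 3 / 3 h, SD 3.2 | 31 | 99.99% | 95.8% | 92.6% |

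The last four rows use the Phase IIa figures quoted in SAP section 4, in the plan's favour. The 4.6 h there refers to ON-time with troublesome dyskinesia, not to the primary endpoint.

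**Step 4: what n would be needed.** With 3 h at every dose and SD 3.5, the 5 mg bound passes 92% at 37 evaluable per arm (92.5%). That allows (38.5 − 37)/38.5 = 3.9% dropout, whereas the SAP reports more than 10%. The 2.5 mg bound passes 92% at 40 per arm (92.5%), which is more than the 38.5 randomized.

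**Step 5: checks.** Simulated t tests with the variance pooled over four arms give 91.7 / 86.0 / 81.6% at n = 31, so the normal figures slightly favour the plan. For illustration only, I simulated the full procedure with both key secondaries given the same standardised effect as the primary (my assumption, correlations 0.3 and 0.6). This gives about 83% for 5 mg and 73–75% for 2.5 mg. At 0.8 of that effect it gives about 72% and 54–56%.

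**The case against.** The best defence is that section 4 speaks of a single dose level against control, which is per-comparison wording, and that the hierarchical clause only explains how the error rate is protected. On that reading 92% is right. Protocol 14.9.4 already had a fixed dose sequence alongside the same 92%, so the SAP merged two statements and added the key-secondary gates. I accept that the figure is not an arithmetic error. But the sentence as written says that the power is obtained with the hierarchy, and the per-comparison reading leads to the same edit.

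The second objection is that 3 h at every dose is not the plan's scenario. The plan expects 7.5 mg to be most effective and cites "a dose dependent effect with an observed difference vs. placebo around 4.6 h at the 7.5 mg dose". This stands as far as size goes. With 4.6 h at 7.5 mg the 5 mg bound returns to 92.1%, and combining that with SD 3.2 puts both lower doses at or above 92%. Those cases are still bounds with the key-secondary gates open, and the plan's own calculation uses SD 3.5.

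Third, the planned test is a baseline-adjusted MMRM that also uses Week 4 and Week 8 data. If 3.5 is an unadjusted SD, that model could do better than a two-sample test on completers. It would raise the stand-alone power too, so the gap between a stand-alone and a gated comparison would remain.

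Last, the harm is limited: SAP 6.12 requires 95% confidence intervals, and 6.15 requires a table of the alpha and decision at each stage. That is correct.

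**Conclusion.** The concern holds. For a lower dose with a 3 h effect, SD 3.5 and 31 evaluable per arm, 92.1% is the ceiling under SAP 6.15 whatever the other doses do. It is reached only if every earlier test is certain to reject. With 3 h at every dose the bounds are 86.6% for 5 mg and 82.3% for 2.5 mg, which are 5.5 and 9.8 points below 92.1%. At 154 randomized with 10% dropout (34.65 per arm) they are 90.6% and 87.3%. The real shortfall depends on the higher-dose effects and on key-secondary effects and correlations. The documents give no inputs for the key secondaries, so they provide no basis for any lower-dose power claim under the procedure. The fault is in what the figure is said to describe; 92% remains right for the 7.5 mg primary.

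**What to change.** In SAP section 4, state that 92% is the power of the 7.5 mg primary comparison, or the unadjusted per-comparison power at two-sided 0.05, and that it does not describe 5 mg or 2.5 mg under 6.15. Add the upper bounds for those two doses with the evaluable n per arm, the effect at each dose and the SD, preferably on the 154 basis as well. In 6.15, limit the clause on maintaining planned power to the 7.5 mg primary. Simulating the full procedure with stated key-secondary assumptions would be useful but is optional.

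The cost is one or two sentences and one clause, and a less favourable stated power for the two lower doses. It needs no extra patients and no change to the testing procedure or to any analysis.
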